##### **C. Study Design and Research Methods**

- a. Currently the standard of care at Hospital Roosevelt is to perform standard blood culture on all specimens that are positive on the automated VIRTUO system. This occurs by trained lab technicians 24/7. Once there is colony growth on the plates via standard culture, the isolate is placed on the VITEK system for identification and susceptibility. This process has been analyzed in the program evaluation and will serve as historical controls.
- b. In this prospective study, we will implement the BioFire FilmArray blood culture identification panel (BCID2), which laboratory technicians will run simultaneously with standard culture after it flags positive on VIRTUO system. We will only run the BCID2 panel on those specimens that become positive during **normal working hours Monday-Friday from 7am to 1pm** due to the inability to staff the laboratory overnight and on weekends. **Those specimens that become positive from 12am to 7am will be run at 7am, as the panel can be run up to 24 hours from positivity per BioFire protocol.** Those that become positive in the evening from 1pm-11:59pm Monday-Thursday will not be run on the BCID2 and will serve as controls. All positive cultures (in both groups) will be plated on agar plates to confirm growth on culture and undergo susceptibility testing per standard current protocols.
- c. Physicians will be notified of panel results, as well as standard culture results per current laboratory protocol, which includes uploading results onto a webpage accessible to all physicians on their mobile device. **BCID2 results will additionally be reported to providers directly by telephone notification or in person by the study PI.** Standard culture results on control patients will be reported per standard protocol of webpage notification.
- d. Antimicrobial stewardship will be continued per current standard of care at Hospital Roosevelt. The Pediatric Infectious Disease fellows and attendings at Hospital Roosevelt review all positive cultures in the microbiology laboratory each morning,

and review results in person with the inpatient teams. **During this study, the local PI will serve as the antimicrobial steward and provide BCID2 results to physicians within 1 hour of notification. We will provide guideline-based recommendations for all BCID2 results to help standardize the stewardship process.**

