**D. Description, Risks and Justification of Procedures and Data Collection Tools:**

The panel will be performed all on positive pediatric blood cultures that are positive during laboratory working hours. The panel results will be released to clinical providers. This is necessary in order to assess the clinical impact and clinical decision-making based on the results. A local investigator will review all positives throughout the day and inform the treatment team of the results. All enrolled patients will undergo chart review to assess for clinical outcomes, such as antimicrobial agents, ICU days, hospital days, and mortality. We will need to collect this information in order to assess the clinical impact of this panel. The information will be stored directly into RedCap database which will be accessible only to key study personnel. The study involves minimal risk to the patient, as it only includes risk of loss of confidentiality. We are requesting a full waiver of informed consent, as subjects will be assigned to the intervention versus control group based on the timing of positive cultures. Patients, providers and investigators will not have control over which patients will be placed into the control or intervention groups, as this will be randomized based on time of positivity. This reflects the reality of laboratory capabilities in low-middle income countries, such as Guatemala.

**E. Potential Scientific Problems:** There will be challenges of working in Guatemala City, as this is a limited-resource setting. The culture around antibiotic usage is different than in the U.S. and therefore may impact the expected reduction in time to effective and optimal antimicrobial therapy. Currently they only obtain a single blood culture bottle during collection, but this is standard in many low-middle income countries.

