**F. Data Analysis Plan:** Hospital Roosevelt has 800 pediatric blood cultures processed monthly (with about 5% positivity). Based on preliminary data, only 37% of patients with positive blood cultures received optimal therapy based on predefined consensus guidelines. Of those who receive optimal therapy, the median time to therapy is 90 hours. With the addition of a blood culture identification panel, we expect to see a reduction in time to optimal antimicrobial therapy to 30 hours. This estimate is based on U.S. data conducted at our institution showing a reduction to 27 hours on average with BCID plus antimicrobial stewardship.

Target Enrollment: 100 patients over 4 month study period

**G. Summarize Knowledge to be Gained:** This study is important to evaluate the impact that rapid multiplex blood culture identification PCR panels have on improving clinical outcomes in low-middle income countries such as Guatemala. It has shown significant impact in reduction in time to optimal antimicrobial therapy in high-income countries. In countries such as Guatemala, with higher rates of antimicrobial resistance and broad-spectrum antimicrobial usage, the potential impact is greater and could lead to a mortality benefit. If a significant clinical impact is observed, we would advocate for continued use of the panel at Hospital Roosevelt, as well as 24/7 implementation if a significant difference is seen between the intervention and prospective control group. This could be translatable to other low-middle income countries.

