Rapid Blood Culture Identification Panel in Pediatric Patients in Guatemala

NCT05314816

Statistical Analysis Plan

v. 2/23/2023

Statistical Analysis Plan

Objective: to evaluate the clinical impact of the BioFire BCID2 panel in children with bacteremia in Guatemala.

Study Design: Pragmatic clinical trial comparing intervention to two different control groups. Intervention and concurrent control group allocated by time of blood culture positivity. Also comparing to historical controls.

Primary outcome: time to optimal antimicrobial therapy

Secondary outcomes:

- Time to effective antimicrobial therapy
- Time to pathogen identification
- Mortality
- Length of hospital stay
- Antibiotic days of therapy (DOT)
- Number of unique antibiotics
- Total ICU days

Definitions to consider:

Patient Group

Intervention= patient was enrolled in the intervention group and received the BCID2 intervention within 12h timeframe

Concurrent control= patient was enrolled in the study and did not receive the BCID2 intervention within 12h from blood culture positivity

- Weekday controls= Patient with positive blood culture from 1pm-11:59pm Mon-Thurs
- Weekend controls= Patient with positive blood culture from 1pm Fri- 11:59pm Sunday

Per protocol =patient received intervention based on original allocation.

- Per protocol intervention= Patient allocated to intervention based on timing of blood culture AND BCID2 was performed within 8h timeframe.
- Per protocol control= Patient allocated to control group based on timing of blood culture AND no BCID2 was performed.

Protocol deviation=Patient intended to remain in the allocated group, but there was an unintentional deviation from protocol.

- Protocol deviation intervention= BCID2 run between 8-12h in patient allocated to intervention.
- Protocol deviation control= BCID2 was sent clinically >12h from positive culture in patient allocated to control group OR patient originally allocated to intervention group but BCID2 was not performed.

Sub-groups

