Clinician discretion (Intention to treat analysis (ITT))=effective and optimal therapy determined based on whether **treating physicians** considered the pathogen real or a contaminant. Optimal therapy allowed additional antibiotics if the treating team was also treating for other syndromic diagnoses, such as culture-negative sepsis (if pathogen detected deemed to be a contaminant), nosocomial pneumonia, etc. if called out in diagnoses. Definitions created for optimal therapy for nosocomial pneumonia, culture-negative sepsis, etc.

- Time to effective therapy in ITT:
 - Time from blood culture received in lab (time 0) to effective therapy
 - Time from blood culture positivity (time 0) to effective therapy
- Time to optimal therapy in ITT:
 - Time from blood culture received in lab (time 0) to effective therapy
 - Time from blood culture positivity (time 0) to effective therapy

Pathogen directed (Per protocol analysis) =effective and optimal therapy based on **strict definitions** for real pathogen or contaminant created by study team. Strict optimal antibiotic definitions without allowing for additional antibiotics for culture-negative sepsis or nosocomial pneumonia, etc. Does allow for additional antibiotics for clear other indications (pyelonephritis, CAP, dacrocystitis, intra-abdominal abscess, etc.) or another organism isolated (excluding urine and trach cultures). Not allowing for more controversial diagnoses such as sepsis or nosocomial pneumonia.

- Time to effective therapy in per protocol:
 - Time from blood culture received in lab (time 0) to effective therapy
 - Time from blood culture positivity (time 0) to effective therapy
- Time to optimal therapy in per protocol:
 - Time from blood culture received in lab (time 0) to effective therapy
 - Time from blood culture positivity (time 0) to effective therapy

Secondary outcomes

Time to pathogen identification= Time from time of blood culture receipt in lab (time 0) to identification of a pathogen. For control patients, this is the time to Vitek. For intervention patients, this is the time to BCID2 if the BCID2 was positive for an on-panel pathogen or time to vitek if the BCID2 was negative.

- Control: time to Vitek
- Intervention:
 - If BCID2 positive → calculate time to BCID2 result
 - If BCID2 negative → calculate time to Vitek

Total antibiotic days=all days that patient was on antibiotics (any dose of antibiotic) from date that blood culture was drawn. Capped at 14 days or date of death.

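### Analysed groups depend on whether BCID2 was run within 12 h, so patients allocated to intervention can be counted as controls and no listed analysis compares patients as allocated

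*SAP*

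**What the plan says.** Protocol section IV.D states that "subjects will be assigned to the intervention versus control group based on the timing of positive cultures", and the SAP's Study Design line agrees.

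The SAP's Patient Group definitions then add a condition that is met or missed only after allocation. For the intervention group the text is "Intervention= patient was enrolled in the intervention group and received the BCID2 intervention within 12h timeframe". The comparator is defined by the absence of a timely run, with no mention of the group to which the patient was allocated: "Concurrent control= patient was enrolled in the study and did not receive the BCID2 intervention within 12h from blood culture positivity".

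Under Protocol deviation, the control category holds two kinds of patient. One is a control-allocated patient whose BCID2 was sent clinically more than 12 h after positivity. The other is a "patient originally allocated to intervention group but BCID2 was not performed". The same block describes a deviation as an unintended departure in a patient who was meant to stay in the allocated group.

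The Overview of Analyses lists a main comparison that keeps deviations in these groups and a per-protocol comparison that removes them. The label ITT is attached to the clinician-discretion definition, which settles who judges the organism and what counts as optimal therapy. It does not settle who is analysed in which group.

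**The concern.** Allocation by positivity time is the design's only protection against selection, because nobody chooses when a bottle flags. Whether and when the panel is then run lies outside that protection. The SAP moves patients on that later event, and in one direction only. Intervention-allocated patients without a timely run become controls, while control-allocated patients with a late clinical BCID2 stay controls.

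No listed analysis repairs this:

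- The main comparison counts the moved patients as controls.
- The per-protocol comparison discards them.
- The weekday and weekend control columns are defined by window (for example "Weekday controls= Patient with positive blood culture from 1pm-11:59pm Mon-Thurs"), so they leave the moved patients out of the comparator but do not return them to intervention.
- The analysis called ITT defines no groups, and its label may lead readers to think an as-allocated analysis exists.

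Two things are at stake. If missed or late runs relate to prognosis or to care, the primary outcome and every secondary outcome in the main comparison are biased. If they do not, the contrast still estimates the effect of BCID2 when run on time, not of the service as allocated. Protocol section IV.G ties its advice to this contrast: "24/7 implementation if a significant difference is seen between the intervention and prospective control group".

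There is also a definitional gap. An intervention-allocated patient run after 12 h is a control by the main definition but fits neither deviation category. For time to pathogen identification the SAP says "For control patients, this is the time to Vitek", so any such patient's actual BCID2 result would be ignored.

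**Working it through.** **Inputs.** SAP Table 2A: per-protocol intervention 112, per-protocol control 192, deviation intervention 23, deviation control 27. SAP Table 2: intervention 135, concurrent control 219, total 354. Protocol section III: 37% reached optimal therapy and 20% died among historical controls. I read the table counts as patients, since the protocol enrols first positive cultures.

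**The plan's own figures.** 112 + 23 = 135; 192 + 27 = 219; 135 + 219 = 354. They reproduce exactly, so the 27 deviation controls sit inside the 219.

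**How many could be moved.** Let k be the number of intervention-allocated patients among the 27. The split is not given, so k runs from 0 to 27. If the 27 hold all moved patients, the groups as allocated are 135 + k v 219 − k, that is from 135 v 219 to 162 v 192. At k = 27, moved patients are 27/219 = 12.3% of analysed controls and 27/162 = 16.7% of intervention-allocated patients.

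**(a) Missed runs unrelated to prognosis; moved patients do as controls do.** Let mI be the mean or proportion in the 135 and mC that in controls. The intervention mean as allocated is (135·mI + k·mC)/(135 + k). Subtracting mC gives an as-allocated difference of (mI − mC) × 135/(135 + k). The received-based difference is therefore (135 + k)/135 times the as-allocated one:

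- k = 0: 1.00
- k = 10: 145/135 = 1.07
- k = 27: 162/135 = 1.20

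**(b) and (c) No true effect, but moved patients differ.** With base rate b in both groups as allocated and rate p in the moved patients:

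- I = ((135 + k)·b − k·p)/135
- C = ((219 − k)·b + k·p)/219

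For example, with b = 0.37, k = 27 and p = 0.20: I = (59.94 − 5.40)/135 = 40.4% and C = (71.04 + 5.40)/219 = 34.9%.

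| Outcome (b) | k | p (assumed) | I | C | Contrast |
|---|---|---|---|---|---|
| Reached optimal therapy (37%) | 10 | 20% | 38.3% | 36.2% | +2.0 points |
| | 10 | 54% | 35.7% | 37.8% | −2.0 points |
| | 27 | 20% | 40.4% | 34.9% | +5.5 points |
| | 27 | 54% | 33.6% | 39.1% | −5.5 points |
| Mortality (20%) | 10 | 10% | 20.7% | 19.5% | risk ratio 1.06 |
| | 10 | 40% | 18.5% | 20.9% | risk ratio 0.89 |
| | 27 | 10% | 22.0% | 18.8% | risk ratio 1.17 |
| | 27 | 40% | 16.0% | 22.5% | risk ratio 0.71 |

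Contrasts are taken before rounding. With k = 0 or p = b there is no distortion.

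**Chance of a false finding.** Use z = |I − C|/√(q(1 − q)(1/135 + 1/219)), with q the pooled rate, and rejection probability Φ(z − 1.96) + Φ(−z − 1.96) at an assumed two-sided 5%. The row k = 27, p = 20% for optimal therapy gives 0.18. The row k = 27, p = 40% for mortality gives 0.315.

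**A check the sponsor can make.** Moved patients turned positive in intervention hours, so they fit neither the weekday nor the weekend control window. The two subgroup sizes, still blank in Table 2, should add to 219 − k (192 to 219) and so reveal k.

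**The case against.** The strongest reply is about reach. At most 27 of 354 patients (7.6%) change group, so at least 92.4% are analysed as allocated. If k = 0, the main comparison already is the as-allocated one. The distortions under no true effect rest on assumed rates, run in both directions, and are small at k = 10. The primary outcome is a censored time to event, and a proportion is only a stand-in for it; the factor in (a) holds for means and proportions, not for medians or hazard ratios. All of this stands. It limits what can be said about size but does not justify the rule, and nothing in the documents shows that k is small.

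A second reply concerns late runs. Protocol section IV.C, item b, says "as the panel can be run up to 24 hours from positivity per BioFire protocol" to explain why overnight positives wait until 7am. It schedules no next-day run for specimens flagged later in the morning. A specimen flagged just before 1pm and run at 7am would be about 18 h old, within that limit yet a control under the SAP, but this is only an illustration. Table 2A gives no sign that such patients exist, so the point on time to identification is conditional. The gap in the definitions remains.

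A third reply is that advice on 24/7 use may reasonably draw on the effect of BCID2 when it is run. It may, as a supplementary estimate. That does not excuse leaving out the contrast that allocation protects.

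Finally, the allocation windows need settling. Protocol section IV.C names only Monday to Thursday afternoon and evening positives as controls, while the SAP adds Friday 1pm to Sunday. The SAP's windows are enough to define an as-allocated control group, and the counts above use them.

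**Conclusion.** The concern holds. As written, the SAP's main comparison groups patients by treatment received, the per-protocol comparison excludes the moved patients, and no listed analysis follows allocation. Confidence is high for the rule itself.

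The extent is bounded but not known: 0 to 27 patients, at most 12.3% of controls and 16.7% of those allocated to intervention, provided the 27 contain every moved patient. Any real difference in a mean or proportion would be inflated by a factor of 1.00 to 1.20 if moved patients do as controls do. Under no effect, the assumed scenarios give shifts of up to 5.5 points either way in reaching optimal therapy, and mortality risk ratios from 0.71 to 1.17. The documents do not say why runs were missed beyond calling the deviations unintended, so the direction of bias cannot be inferred. Because the rule governs the primary comparison, it must be fixed even if k turns out to be small.

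**What to change.** 1. Define the primary comparison by positivity window alone, whether or when BCID2 was run, and reserve the name ITT for it. State that Friday 1pm to Sunday positives are allocated controls, as in the SAP, and reconcile the protocol with this.
2. Report the 27 deviation controls by original allocation and by reason for the missed or late run. State where intervention-allocated runs after 12 h are counted, and likewise control-allocated patients with BCID2 within 12 h, who now fit neither group.
3. Keep the 12 h received-based set and the 8 h per-protocol set as sensitivity analyses.
4. Score time to identification by the first actual result, BCID2 or Vitek, whatever the group.
5. Rename the clinician-discretion and pathogen-directed outcome definitions so that ITT and per protocol refer only to analysis sets.

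The cost is SAP wording and one recoded group variable; positivity time is already held. The downside is that, if missed runs are unrelated to prognosis and moved patients do as controls do, the estimated difference shrinks to 135/(135 + k) of the received-based one, or 135/162 = 0.83 at k = 27.

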### I. Hypotheses and Specific Aims:

1. Primary Aim: The primary aim of this study is to assess the clinical impact of a rapid multiplex PCR blood culture identification panel on time to optimal antimicrobial therapy when compared to conventional microbiological culture methods in children hospitalized in a low resource setting in Guatemala City.
2. Secondary aims:
  - a. To assess the impact of the blood culture identification panel on reduction in time to organism identification when compared to conventional microbiological culture methods
  - b. To assess the impact of the blood culture identification panel on time to effective antimicrobial therapy, mortality, length of stay, and ICU days.
3. We hypothesize that we will see an overall reduction in time to optimal antimicrobial therapy following implementation of the panel.

**II. Background and Significance:** There are high rates of blood culture positivity and antimicrobial resistance in Latin American countries, with high rates of broad-spectrum antimicrobial utilization. Based on our preliminary analysis of pediatric blood cultures at Hospital Roosevelt, the rates of carbapenem-resistant *Klebsiella* and *Acinetobacter* are 65% and 90%, respectively. Because of this, patients are often started empirically on broad-spectrum antibiotics until the organism and susceptibility results are identified. Rapid microbiology diagnostics, such as the Biofire Film Array BCID, have been shown to greatly impact clinical care in high-income countries. The best strategies for implementation and their potential clinical impact in low-middle income countries, however, have not been well defined. Hospital Roosevelt in Guatemala City is a 900-bed public hospital with 180 beds dedicated to pediatric patients. It serves 53% of children in the larger metropolitan area of Guatemala. Co-investigator has a long-standing relationship with Hospital Roosevelt and has partnered with Hospital Roosevelt on previous research studies. PI has an active research study at Hospital Roosevelt involving rapid diagnostics for Pneumococcal disease.

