On-panel true pathogens= Pathogens on the BCID2 panel that are always considered real pathogens per protocol. These include, *E. faecalis*, *E. faecium*, *Listeria*, *Staph aureus*, *Strep pneumonia*, *Strep agalactiae*, *Strep pyogenes*, *Acinetobacter baumannii*, *B. fragilis*, *Enterobacterales*, *Enterobacter cloacae*, *E. coli*, *Klebsiella aerogenes*, *Klebsiella oxytoca*, *Klebsiella pneumoniae*, *Proteus*, *Salmonella*, *Serratia matcescens*, *Haemophilus influenza*, *Neisseria meningitidis*, *Pseudomonas aeruginosa*, *Stenotrophomonas maltophilia*, *Cryptococcus*, *Candida species*.

Gram negative on-panel pathogen= On-panel true pathogens as above that are Gram negatives only. These include *Acinetobacter baumannii*, *B. fragilis*, *Enterobacterales*, *Enterobacter cloacae*, *E. coli*, *Klebsiella aerogenes*, *Klebsiella oxytoca*, *Klebsiella pneumoniae*, *Proteus*, *Salmonella*, *Serratia matcescens*, *Haemophilus influenza*, *Neisseria meningitidis*, *Pseudomonas aeruginosa*, *Stenotrophomonas maltophilia*.

Gram negative pathogen= On or off-panel pathogens that are Gram negatives.

On-panel classic contaminant= Gram positive pathogens on the BCID2 panel that are often considered contaminants (note, may be considered real in the analysis). These include, *Staph epi*, *Staph lugdunensis*, *other Staph species*, *other Strep species*.

Off-panel non-Gram negatives (other)= typically contaminants.

True pathogens (on and off panel)= excluding common contaminants.

Polymicrobial= More than one organism was detected by BCID2 and/or Vitek.

Primary outcomes

Optimal antibiotic=typically narrowest spectrum agent based on predefined consensus guidelines

Effective antibiotic= any antibiotic susceptible based on susceptibilities even if overly broad.

Time to optimal antimicrobial therapy=time blood culture received in lab to time of first dose of “optimal” antibiotic. Censor at 14 days. Censor for death if “never reached” optimal. Stoppage of antibiotics if deemed a contaminant.

Time to effective antimicrobial therapy= time of blood culture received in lab to time of first dose of “effective” antibiotic. Censor at 14 days. Censor for death if “never reached” effective. Stoppage of antibiotics if deemed a contaminant.

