Antibiotic days of therapy =Sum of antibiotics each day over 14-day period. For example if 2 antibiotics were each given over 5 days, this would count as 10 DOT.

Number of different antibiotics=Number of unique antibiotics given over the 14-day period.

Length of stay=date admitted to date patient left the study (date of death/discharge or lapse of 30 days). Censor at 30 days.

Total ICU days=date admitted in ICU to date transferred out or date of death/discharge. Censor at 30 days.

Time to death= Time from blood culture obtained to time of death.

Number of deaths within 24h of blood culture draw= Use time of death calculation above to determine the number of patients who died <24h

Overview of Analyses to perform:

- All interventions vs. all concurrent controls (including protocol deviations) vs. historical controls
 - Demographics
 - All outcomes (primary and all secondary endpoints)
 - Sensitivity analysis comparing weekday vs. weekend controls
- Per protocol controls vs. per protocol intervention (excluding protocol deviations)
 - Demographics
 - All outcomes (primary and all secondary endpoints)
- Clinician discretion (ITT) analysis (controls vs. interventions)

- Number of contaminants vs. true pathogens
- Time to optimal therapy
- Time to effective therapy
- Pathogen directed (Per protocol) analysis (controls vs. interventions)
 - Number of contaminants vs. true pathogens
 - Time to optimal therapy
 - Time to effective therapy
- Gram negatives only (on- and off- panel)
 - Demographics
 - Time to optimal therapy
 - Time to effective therapy
 - Mortality
- On-panel true pathogens only
 - Demographics
 - Time to optimal therapy
 - Time to effective therapy
 - Mortality
- On-panel Gram negatives only
 - Demographics
 - Time to optimal therapy
 - Time to effective therapy
 - Mortality
- True pathogens (on and off panel)
 - Demographics
 - Time to optimal therapy
 - Time to effective therapy
 - Mortality

Figure 1: CONSORT Diagram

Table 1: Patient Characteristics

*Wilcoxon test of medians

**chi-square test

Table 1A: Supplemental table with demographics from sub-groups.

	Per protocol Intervention	Per protocol Control	p-value	True on-panel pathogen Intervention	True on-panel Pathogen controls	p-value	All Gram negative (GN) Interv.	All GN control	p-value	All GN weekDAY controls	p-value (compare to GN interv.)	On-panel GN Interv.	On-panel GN control	p-value

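### The SAP dates optimal therapy at the first dose of an agent but judges optimality on the whole regimen, so the primary event time is inconsistent for true pathogens treated with combinations

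*SAP*

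**What the plan says.** Under Primary outcomes, the SAP describes the optimal antibiotic as "typically narrowest spectrum agent based on predefined consensus guidelines". Time to optimal therapy runs from "time blood culture received in lab to time of first dose of" that antibiotic, with censoring at 14 days and for death if it is never reached. One other event appears in the same definition: "Stoppage of antibiotics if deemed a contaminant".

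The SAP then gives two scoring versions, and both look beyond the single agent.

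- Clinician discretion (labelled ITT): "Optimal therapy allowed additional antibiotics if the treating team was also treating for other syndromic diagnoses".
- Pathogen directed (labelled per protocol): "Strict optimal antibiotic definitions without allowing for additional antibiotics for culture-negative sepsis or nosocomial pneumonia, etc". An exception follows: "Does allow for additional antibiotics for clear other indications", or for another isolated organism, with urine and tracheal cultures excluded.

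Under each version, the two bullets headed time to optimal therapy name effective therapy as the end point. That makes four such bullets.

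The Protocol's Background section explains why combinations matter here: "patients are often started empirically on broad-spectrum antibiotics until the organism and susceptibility results are identified".

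**The concern.** A first-dose time stamp suits time to effective therapy, because the SAP counts an effective drug even when it is overly broad. It does not suit an outcome under which an unjustified companion drug makes the therapy non-optimal. In that case therapy can become optimal by stopping a drug, with no new first dose to date it.

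Narrowing therapy after organism identification is one of the main actions a rapid panel could speed up. If children already on the optimal agent are timed at its first dose, their event time is fixed before any panel or culture result. It is then the same in both groups whatever the panel does. Abstractors who follow different parts of the SAP could also record different primary event times from one chart. If historical and trial charts were scored under different readings, that comparison would be biased as well.

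**Working it through.** **Step 1. The rules side by side, for a true pathogen.** Take a hypothetical child who receives A and B from about time 0. A alone is optimal for the isolate, B has no other indication, and B is stopped on day 3.

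| Rule in the SAP | What it implies |
|---|---|
| Time to optimal therapy: first dose of the optimal agent | Event at about 0 h, or before receipt if A was begun earlier |
| Scoring versions: additional antibiotics only if allowed | Not optimal until B stops, on day 3 |
| Stop event | Written only for contaminants |
| Time-to-optimal bullets in both versions | End at effective therapy, so they do not settle it |

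The scoring versions decide whether therapy qualifies as optimal. They supply no time stamp to replace the first dose. No rule covers a first dose given before time 0, and this could arise more often in the analyses that start the clock at culture positivity.

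**Step 2. Inputs for an illustration.** The Protocol's Data Analysis Plan gives a median of 90 h among historical patients who reached optimal therapy, and expects 30 h with the panel. The planned difference is 90 − 30 = 60 h. The share *f* already on the optimal agent within a combination is not in the documents. I assume *f* = 10%, 20% and 40% of those who reach the endpoint, equal in both groups. I treat 90 h and 30 h as the regimen-based medians, which is also an assumption.

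**Step 3. Exponential times, with the share *f* scored at 0.** The median solves (1 − f) × 2^(−x/m) = 0.5, so x = m × [1 + log2(1 − f)].

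- f = 10%: factor 0.848; 90 × 0.848 = 76.3 h and 30 × 0.848 = 25.4 h; difference 50.9 h.
- f = 20%: factor 0.678; 61.0 h and 20.3 h; difference 40.7 h.
- f = 40%: factor 0.263; 23.7 h and 7.9 h; difference 15.8 h.

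**Step 4. Lognormal times (log-scale SD 0.8), with the share *f* scored between 0 and 6 h.** The median is x = m × exp(0.8 × z), where Φ(z) = (0.5 − f)/(1 − f).

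- f = 10%: z = −0.140, factor 0.894; 80.5 h and 26.8 h; difference 53.7 h.
- f = 20%: z = −0.319, factor 0.775; 69.7 h and 23.2 h; difference 46.5 h.
- f = 40%: z = −0.967, factor 0.461; 41.5 h and 13.8 h; difference 27.7 h.

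Controls scored optimal by 24 h: Φ[ln(24/90)/0.8] = 4.9% at f = 0. The formula f + (1 − f) × 4.9% then gives 14%, 24% and 43%.

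**Step 5. What this does to a test.** In both models the ratio of medians stays at 3, because one factor multiplies both groups. The log-rank signal does weaken. I simulated the lognormal model with the group sizes in the SAP tables, 135 and 219. If every child would eventually reach the endpoint, the mean absolute z falls from 11.7 at f = 0 to 6.0 at f = 40%, and power stays near 100%. If only 37% reach it in both groups (apart from the share *f* of all children scored early), power is about 23% at f = 0 and falls to about 7–9% at f = 40%.

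**The case against.** A reader might infer that children on the agent within a broad combination are counted as early successes. The documents do not support that as fact. The limits on additional antibiotics make sense only if an unjustified companion drug prevents therapy from being optimal. The consensus guidelines that the SAP cites are not reproduced in it, and they may contain a regimen rule.

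A reader might also infer that de-escalation by stopping drugs is not measured. That is too broad. Stopping is the event for contaminants, and a switch from a broad agent to a new narrow one is dated by its first dose. Antibiotic days of therapy, defined as "Sum of antibiotics each day over 14-day period", fall when companion drugs are withdrawn. They cannot, however, say when therapy became optimal.

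The historical figures fit poorly with many time-zero successes: only 37% reached optimal therapy, at a median of 90 h. They do not show which rule was applied. If 90 h was itself a first-dose figure, any distortion is already inside it.

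The numerical objections also stand. The share *f* is assumed, the median calculations describe only children who reach the endpoint, and the ratio of medians does not change. None of this supplies the missing event time for a true pathogen when therapy becomes optimal because a drug is stopped.

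**Conclusion.** The point holds as an inconsistency in the definition of the primary event time. It is confined to true pathogens in children already receiving the optimal agent together with a drug that the scoring version does not allow. For them the one written time stamp contradicts the regimen criterion. Followed literally, it gives a time near or before 0, which attenuates the group difference in time.

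The size is unknown. Across the two models, a 60 h difference becomes about 51–54 h at a 10% share, 41–47 h at 20% and 16–28 h at 40%. These figures rest on an assumed share that is equal in both groups, on assumed distributions, and on reading 90 h and 30 h as regimen-based medians. They show direction and plausible scale. They do not estimate bias in this trial, and the documents do not show that the first-dose rule was in fact applied to such children.

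Because the primary event time is not uniquely defined, this should be settled before the primary comparison is relied on.

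**What to change.** 1. In the SAP's definition of time to optimal therapy, date the event for true pathogens at the first time, at or after time 0, when the regimen contains the optimal agent(s) and no antibiotic disallowed by the scoring version in use. For a combination, this is the later of the first optimal dose and the stop of the last non-allowed drug.
2. State how a regimen already optimal at time 0 is scored, for each time 0 in use.
3. State how a child is scored who leaves the optimal agent and later returns to it. More than one rule is defensible, so the study team should choose one and write it down.
4. Apply the same rule to the intervention, concurrent control and historical groups. Report how many children in each group have different times under the two rules, since that count gives the share that is unknown here.
5. Keep first-dose time as a sensitivity analysis.
6. Correct the four time-to-optimal bullets that end at effective therapy.

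This changes only how charts are scored, not treatment. The cost is SAP wording and re-derivation of one variable. Days of therapy already need daily drug records, and the contaminant rule already needs stop times. The drawback is that precision will depend on charted stop times, and some children will move to a later time or to never reached.
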